3.4 Discontinuation/Withdrawal

3.4.1 Discontinuation Criteria

Study intervention will be discontinued if subject is unable to tolerate the tPCS or Melatonin.

3.4.2 Discontinuation Visit and Procedures

Subjects may withdraw voluntarily from participation in the study at any time. If withdrawal occurs, subjects will still be asked to complete a questionnaire to study the reason for withdrawal. Actigraphy will be done (if any) to the point of withdrawal from participation in the study.

4 TRIAL MATERIALS

4.1 Trial Product (s)

HSA CRM notification

The tPCS is an electrical and neuromuscular stimulator classified as a general medical device. Clinical Research Material Notification from Health Science Authority Singapore has been obtained.

Refer Annex B for picture of device.

Technical Information of the tPCS (AscenZ-IV Multi-channel Pulsed Current Stimulator; Yiqi Biotechnology Co. Ltd., China):

- Intensity: 0.7-1mA
- Waveform: Monophasic square wave
- Pulse width: 140 μ s
- Frequency: 400Hz
- Electrode materials: self-adhesive silica gel patch
- Electrode size: 5*5cm

5 TREATMENT

5.1 Rationale for Selection of Dose of Intervention

- 1) Based on safety recommendations of TES in children, reduced (~1 mA) current intensities are often used, but trials up to 2 mA without serious adverse effects are reported [42].
- 2) A study period of 20 sessions of 45 minutes duration is based on manufacturer's clinical experience, unpublished data.

5.2 Intervention settings

The intervention is the tPCS and it will be administered by trained personnel of the industrial partner. .

5.3 Intervention Administration

45min/ session of tPCS will be performed at home, supervised by a trained personnel, Monday to Friday for 20 sessions over 4 weeks in each sequence period.

5.4 Specific Restrictions / Requirements

Nil as long as exclusion criteria is not met.

5.5 Blinding

Blinding is not done to the patients. Only the study member reporting the actigraphy, and the study member performing data analysis will be blinded.

5.6 Concomitant therapy

Subjects can continue regular standard care.

6 SAFETY MEASUREMENTS

6.1 Definitions

An adverse event (AE) is any untoward medical occurrence in a patient or clinical investigation subject administered a pharmaceutical product and which does not necessarily have a causal relationship with this treatment. An adverse event (AE) can therefore be any unfavourable and unintended sign (including an abnormal laboratory finding), symptom, or disease temporally associated with the use of a medicinal (investigational) product, whether or not related to the medicinal (investigational) product.

A serious adverse event (SAE) is any untoward medical occurrence that at any dose:

- results in death
- is life-threatening
- requires inpatient hospitalisation or prolongation of existing hospitalisation
- results in persistent or significant disability/incapacity, or
- is a congenital anomaly/birth defect

6.2 Collecting, Recording and Reporting of Serious Adverse Events (SAEs) to CIRB

Only related SAEs (definitely/ probably/ possibly) will be reported to CIRB. Related means there is a reasonable possibility that the event may have been caused by participation in the clinical trial. Please refer to the CIRB website for more information on Reporting Requirement and Timeline for Serious Adverse Events.

The investigator is responsible for informing CIRB after first knowledge that the case qualifies for reporting. Follow-up information will be actively sought and submitted as it becomes available.

Related AEs will not be reported to CIRB. However, the investigator is responsible to keep record of such AEs cases at the Study Site File.

6.3 Collecting, Recording and Reporting of Serious Adverse Events (SAEs) to the Health Science Authority (HSA)

All SAEs that are unexpected and related to the study drug will be reported to HSA. Please refer to the HSA website for more information on Safety Reporting Requirements for Clinical Trials.

6.4 Safety Monitoring Plan

All data will be entered into a secure password-protected document in the desktop. Access to the data will only be open to the study investigators. Hardcopy of the data forms will be stored in a locked cupboard in the department.

All adverse events of tPCS in all participants will also be logged and safety of tPCS will be monitored by the principal investigator.

6.5 Complaint Handling

If there is any complaint of the tPCS, the Principal Investigator will be informed immediately to rectify the issue. If the subject is unable to tolerate the tPCS, the study will be discontinued.

7 DATA ANALYSIS

7.1 Data Quality Assurance

The Principal Investigator will ensure accuracy of the data entered. Identifiable patient data will be anonymised. Access to the data will only be open to the investigators in the team.

7.2 Data Entry and Storage

All data will be entered into a secure password-protected document in the desktop. Access to the data will only be open to the study investigators. The Principal Investigator will ensure accuracy of the data entered. Hardcopy of the data forms will be stored in a locked cupboard in the department.

8 SAMPLE SIZE AND STATISTICAL METHODS

8.1 Determination of Sample Size

In an inequality test on data from the Balaam's crossover design, a sample size of 32 achieves 83% power at a 5% significance level when the absolute difference between the two treatment means is 0.2 and the within-subject standard deviation is 0.15. To account for 20% drop-out rate, a sample size of 40 (10 in each arm) is required.

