1.4 Primary Objectives

The primary objective is to assess the effectiveness of tPCS in improving total sleep time by 20% in children with neurodevelopmental disorder, compared with using Melatonin.

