2 STUDY POPULATION

2.1 List Number and Nature of Subjects to be enrolled

[figure not shown]
Based on a two-sided paired t-test at 80% power and 5% one-sided alpha with 20% drop-out rate, a sample size of 40 is required to detect 20% improvement in primary end-point (total sleep time), assuming 15% standard deviation.

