2.1 Sleep disturbance scale for children (SDSC) and Aberrant Behavior Checklist (ABC)

2.2 WHO International Classification of Functioning, Disability and Health, Children & Youth version (ICF-CY) sleep ratings

³Actigraphy. Participants will collect the Actiwatch and wear it for 1 week at home for whole night actigraphic data at start of the sequence period (Week 0 and Week 6) and at the end of the sequence period (Week 4 and Week 10). Patients will return the Actiwatch at the end of the study.

⁴Transcranial Pulsed Current Stimulation (tPCS) – for intervention arm. 45min/ session of tPCS will be performed at home, supervised by a trained personnel, Monday to Friday for 20 sessions over 4 weeks in each sequence period. Participants will be asked to fill out the compliance/ adverse event log daily.

⁵In the control group, participants will be given Melatonin over 4 weeks in each sequence period. They will be asked to fill out the compliance/ adverse event log daily.

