3.3.2 Study Visits and Procedures

Baseline

Prior to commencement of intervention, the patient will undergo:

I. Actigraphy

Actigraphy is a method used to study sleep-wake patterns and circadian rhythms by assessing movement, most commonly of the wrist.^{xxxviii} We will be collecting whole night actigraphic data using Actiwatch (Actiwatch 2, Resironics, USA), worn on the nondominant wrist or ankle – 7 days before intervention commences and in the last week of intervention/control. The four sleep statistics include total sleep time [TST (min)], sleep onset latency [SOL or period of time between bedtime and sleep start (min)], sleep efficiency [percentage of time in bed actually spent sleeping (%)], and wake after sleep onset (WASO) [the time in a sleep interval scored as wake (min)].

II. Sleep disturbance scale for children (SDSC) questionnaire

The SDSC is a 26-item questionnaire that evaluates sleep disturbances including sleep CR initiation/maintenance, breathing, arousal, transitions, daytime sleepiness and sweating in children.^{xxxix}

III. Aberrant Behaviour Checklist (ABC)

The ABC is a behavior rating scale for the assessment of treatment effect. It consists of five factors including (i) Irritability, Agitation, Crying; (ii) Lethargy, Social withdrawal; (iii) Stereotypic behaviour; (iv) Hyperactivity, Non-compliance; and (v) Inappropriate Speech. This will only be used for participants with autistic spectrum disorder.

IV. ICF-CY sleep ratings

Using the WHO International Classification of Functioning, Disability and Health, Children & Youth version (ICF-CY) in the domain of Body Structure/ Function, sleep is evaluated in four aspects: amount of sleep (B1340), onset of sleep (B1341), maintenance of sleep (B1342) and quality of sleep (B1343).¹⁷ Levels of ICF-CY impairment was graded according to frequency, intrusiveness or severity: from 0 (no impairment/ difficulty) to 4 (complete/ constant impairment/ difficulty/ intensity totally disruptive).¹⁸

V. EQ5D

Quality of life measures will be collected and compared between groups.

Intervention

Throughout the intervention period of 6 weeks, patients from the intervention arm will be receiving tPCS, 0.7-1mA for 45 min/ day Monday to Friday (non-public holiday) over 4 weeks in each sequence period. Any adverse event will be recorded in the adverse event log.

Post-intervention

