8.2 Statistical and Analytical Plans

The SPSS® 25.0 software (IBM, Armonk, New York, United States) will be used, with statistical significance defined as a p-value of <0.05 . Independent t-tests will be conducted to compare differences in outcomes between the two treatment groups; Wilcoxon signed-rank test will be used to compare continuous variables at start and end of treatment. Average of actigraphic measurements were used to compare effects of treatment on sleep parameters. One-way Repeated Measure ANOVA will be conducted to assess changes in outcomes and patient scores within the group across the timepoints. Non-parametric testing will also be conducted to observe for significant differences in patient outcomes within the groups at each timepoint.

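### The 20% effect and 15% SD are not tied to a defined primary variable, and the stated 83% power holds only on some readings of them and only one-sided

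*Protocol*

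**What the plan says.** - Section 8.1 (sample size) claims that "a sample size of 32 achieves 83% power at a 5% significance level". The effect and spread behind that claim are given as follows: "the absolute difference between the two treatment means is 0.2 and the within-subject standard deviation is 0.15". It names no unit, variable or reference mean, and does not say whether the 5% is one- or two-sided. The 32 become 40 after 20% drop-out.
- Section 2.1 justifies the same 40 children as the number "to detect 20% improvement in primary end-point (total sleep time), assuming 15% standard deviation". The test there is described thus: "Based on a two-sided paired t-test at 80% power and 5% one-sided alpha with 20% drop-out rate".
- Section 1.4 (primary objective): "improving total sleep time by 20% in children with neurodevelopmental disorder, compared with using Melatonin".
- Section 3.3.2 lists the actigraphy endpoint in minutes: "total sleep time [TST (min)]".
- The actigraphy footnote to the visit schedule in section 3.3 has the watch worn "at start of the sequence period (Week 0 and Week 6) and at the end of the sequence period (Week 4 and Week 10)".
- Section 8.2 sets significance at p < 0.05 and compares the treatments by independent t-tests on outcomes. It adds that "Wilcoxon signed-rank test will be used to compare continuous variables at start and end of treatment", and says that averaged actigraphy is used to compare treatment effects. It does not say whether the treatment comparison is made on minutes, change or ratio.

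**The concern.** Power depends on the effect divided by the SD, and both must belong to the variable that is tested. The protocol leaves at least three candidates open: the end-of-period value as a fraction of some common mean, the ratio of tPCS to Melatonin, and the change from the start of each period. The objective's wording points to a ratio, or to an improvement compared between treatments. The schedule, with actigraphy at both ends of each period, makes a change analysis easy to choose.

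The same pair, 0.2 and 0.15, does not give the same power on all three. This is the trial's only sample-size justification, so a reader cannot tell whether the trial has the 83% it claims. The open sidedness adds a second uncertainty of about ten points.

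**Working it through.** **Inputs.** N = 32 evaluable, 8 per sequence over four sequences; difference 0.2; within-subject SD s = 0.15; 5% level (all section 8.1). Section 1.2.4 justifies Balaam's design by unbiasedness under unequal carryover, so the carryover-adjusted variance is used.

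**Formula.** SE = s × √(2/n) with n per sequence, which equals s × √(8/N). Noncentrality = difference / SE. Degrees of freedom = 4n − 3 = 29. Power is from the noncentral t distribution.

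**Step 1: the protocol's own figure.** SE = 0.15 × √(8/32) = 0.075; noncentrality = 0.2/0.075 = 2.667. Power is 83.1% at one-sided 5% and 73.2% at two-sided 5%. The stated 83% therefore reproduces, but only one-sided. Drop-out: 32/(1 − 0.2) = 40, which also reproduces.

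**Step 2: minutes.** If both inputs are fractions of one reference mean, the mean cancels. With an assumed mean of 480 min, 0.2 and 0.15 become 96 and 72 min, and power is still 83.1% one-sided. The same holds for assumed means from 360 to 540 min.

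**Step 3: 20% as a ratio to Melatonin.** On the log scale the difference is ln 1.2 = 0.182. A coefficient of variation of 15% gives a log SD of √ln(1 + 0.15²) = 0.149. SE = 0.149 × 0.5 = 0.0746; noncentrality = 2.445. Power is 77.1% one-sided and 65.7% two-sided. With log SD 0.15 instead, it is 76.7% and 65.2%. No baseline adjustment is included.

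**Step 4: change from period baseline.** Assume that 0.15 is the SD of a single measurement, equal at the start and end of a period, with error correlation r between the two. Then the SD of change = 0.15 × √(2(1 − r)).

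| r | SD of change | Noncentrality | Power, one-sided | Power, two-sided |
|---|---|---|---|---|
| 0 | 0.212 | 1.886 | 57.8% | 44.6% |
| 0.25 | 0.184 | 2.177 | 68.5% | 55.8% |
| 0.5 | 0.150 | 2.667 | 83.1% | 73.2% |
| 0.75 | 0.106 | 3.771 | 97.9% | 95.4% |

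The protocol gives no value for r, so the whole range is shown.

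**The case against.** The strongest reply is that section 2.1 supplies the missing scale. It gives the inputs as percentages, so 0.2 and 0.15 in section 8.1 can be read as proportions, and step 2 shows that moving from proportions to minutes costs nothing. This stands. A reader might infer that the figures are unit-free throughout, or that an endpoint in minutes by itself invalidates the power; the documents support neither.

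A reader might also infer that analysing change or percentage change necessarily doubles the variance and pulls power down to 58%. That does not follow. The protocol never says that 0.15 is the SD of a single measurement. If it is already the SD of the change, or if r is 0.5, the 83% one-sided is intact, and above 0.5 power is higher. Nor is a change analysis clearly planned: the Wilcoxon sentence in section 8.2 is a start-to-end comparison, not the between-treatment contrast, and the sentence on averaged actigraphy fits a comparison of TST values.

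The shortfalls also depend on keeping the carryover term. Without it, the unadjusted inputs give 97.9% one-sided and 95.4% two-sided, the ratio reading (log SD 0.15) 95.7% and 91.3%, and the change reading at r = 0 gives 83.1% and 73.2%. But the carryover-adjusted variance is the one that reproduces the protocol's 83% and matches its reason for choosing the design.

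Finally, transformation and covariates may be left to a statistical analysis plan, which is not at hand. That is fair for modelling detail. It does not cover a power statement whose inputs the protocol itself gives without saying what they measure.

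**Conclusion.** The point holds as a defect of definition with conditional consequences for power. It is not an arithmetic error: the 83% is correct for a difference of 0.2 and an SD of 0.15 on one common scale at one-sided 5%.

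What is missing is the reference for the 20%, the variable to which the 15% belongs, and a consistent statement of sidedness. Under the carryover-adjusted variance with 32 completers:

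- a two-sided 5% test lowers 83% to 73% on the protocol's own inputs;
- a ratio of 1.2 to Melatonin, a direct reading of the objective, gives about 77% one-sided and 66% two-sided, below both the 83% of section 8.1 and the 80% of section 2.1;
- a change analysis may give anything from 58%/45% at r = 0 to 83%/73% at r = 0.5 or more beyond that, if 0.15 is a single-measurement SD.

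The protocol does not allow a choice among these, so the stated power cannot be relied on until the variable is named. The point should be corrected, with medium confidence in the size of any loss.

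**What to change.** In sections 8.1, 8.2 and 2.1, use one definition throughout:

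1. Name one primary variable. Log of the 7-night mean TST at the end of each period is a good choice, because 20% compared with Melatonin is then a ratio of 1.2.
2. Include the week 0 or week 6 value as a covariate, in place of unadjusted t-tests or change scores.
3. State the scale and source of the 15% SD.
4. State whether the 5% is one- or two-sided, and remove the mixed wording in section 2.1.
5. Restate the difference, SD and power on that basis.

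The cost is wording, a little more analysis work and a probably less favourable power figure. The baseline values are already collected, and no extra patients are needed if the sponsor accepts the restated power. The gain from the covariate cannot be computed here, because the documents give no correlation. For scale, restoring 83% on the unadjusted log scale (SD 0.15) would take 40 evaluable children (40/0.8 = 50 enrolled) one-sided, or 48 (48/0.8 = 60) two-sided.

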8.2 Statistical and Analytical Plans

The SPSS® 25.0 software (IBM, Armonk, New York, United States) will be used, with statistical significance defined as a p-value of <0.05 . Independent t-tests will be conducted to compare differences in outcomes between the two treatment groups; Wilcoxon signed-rank test will be used to compare continuous variables at start and end of treatment. Average of actigraphic measurements were used to compare effects of treatment on sleep parameters. One-way Repeated Measure ANOVA will be conducted to assess changes in outcomes and patient scores within the group across the timepoints. Non-parametric testing will also be conducted to observe for significant differences in patient outcomes within the groups at each timepoint.

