1.2.4 Rationale for Study Design

The unique Two-Period, Four-Sequence (Balaam's) design is used in this crossover trial in which each subject serves as his or her own control. Therefore the estimated treatment differences tend to have less variability than that observed in a parallel design. Smaller variability leads to a smaller sample size. Also, the repeated- measurements feature of a crossover design eliminates the need for a lengthy run-in or baseline period. Moreover, Balaam's design is a hybrid of a crossover design and a parallel design, whereby the estimated treatment difference is unbiased even in the presence of unequal carryover

effects.^{xxxvii}

HYPOTHESIS AND OBJECTIVES

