3 STUDY DESIGN

Figure C: Study Design

At baseline (week 0), all patients will do a one-week sleep actigraphy and complete SDSC questionnaire. At week 1, patients will be randomised to one of the 4 treatment regimen that is determined by the first period of the sequence they are assigned to. Re-evaluation with sleep actigraphy and SDSC questionnaire will be done at week 4, 6 and 10. At week 7, the patients will cross over to the treatment for the second period of the sequence they are assigned to. Over the 10-week period, sleep diary will also be completed daily.

10 patients will receive dose-appropriate Melatonin over 8 weeks (Group A), 10 patients will receive 40 sessions of home-based tPCS over 8 weeks (Group D), 10 patients will receive 4 weeks of Melatonin then cross over to receive 4 weeks of 20 sessions of home-based tPCS (Group B) and 10 patients will receive 4 weeks of 20 sessions of home-based tPCS then cross over to receive Melatonin over 4 weeks (Group C).

There will be a washout period of 2 weeks (week 5 and 6) between cross over. Those on a Melatonin group cross over will also go through the same washout period.

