3.1 Randomisation and Blinding

Randomisation will be conducted for the patients in a 1:1 ratio to two treatment groups in two sequence periods.

Randomisation will be carried out by one study team member uninvolved in the final data analysis. The study member reporting the actigraphy, and the study member performing data analysis will be blinded.

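### The only planned test of tPCS against melatonin is an independent t-test, which is neither the Balaam test powered in 8.1 nor the paired t-test named in 2.1

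*Protocol*

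**What the plan says.** The primary objective (1.4) compares tPCS with melatonin on total sleep time (TST). Three places in the protocol bear on the test for it.

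- **2.1** sets the number of children: "Based on a two-sided paired t-test at 80% power and 5% one-sided alpha", giving 40 after dropout.
- **8.1** sets the same number differently: "In an inequality test on data from the Balaam's crossover design", 32 evaluable children have 83% power at 5% for a difference of 0.2 with within-subject SD 0.15. Dropout of 20% raises this to 40, ten per arm.
- **8.2** states the analysis: "Independent t-tests will be conducted to compare differences in outcomes between the two treatment groups". Its other methods do not compare treatments: "Wilcoxon signed-rank test will be used to compare continuous variables at start and end of treatment", and the repeated-measures ANOVA and further non-parametric tests are within group.

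Section 1.2.4 justifies the Balaam design because each child is its own control and because "the estimated treatment difference is unbiased even in the presence of unequal carryover" effects. In section 3, "patients will be randomised to one of the 4 treatment regimen": melatonin twice (A), melatonin then tPCS (B), tPCS then melatonin (C), tPCS twice (D). Section 3.1 instead describes randomisation "in a 1:1 ratio to two treatment groups in two sequence periods".

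**The concern.** A power figure holds for one test on one set of data. Here the figure is computed for a crossover contrast built on within-child variation, while the listed test treats its observations as independent. On raw values that test also carries the variation between children.

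The two treatment groups of 8.2 are not mapped onto the four sequences. Children in B and C belong to both treatments, and children in A and D contribute twice to one. The t-test has no term for child, period or carryover, so the features that motivated the design are not used.

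Two things are at stake. The stated power may be wrong for the analysis that is run, and several versions of that analysis with very different power remain open, so the choice could be made after the data are seen.

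**Working it through.** **Inputs from 8.1:** difference 0.2, within-subject SD 0.15, 32 completers (8 per sequence), 5% level. **Assumptions:** the protocol does not give the correlation rho between a child's period values, so a range is shown. Covariance is exchangeable, with total variance 0.15²/(1 − rho). Power is from the noncentral t distribution, two-sided unless stated.

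**1. The plan's own figure.** Let d be the second-period minus first-period value, averaged within each sequence. The Balaam contrast is ½[(d_B − d_A) − (d_C − d_D)]. Within each bracket the first treatment is the same, so its carryover cancels. SE = 0.15 × √(2/8) = 0.075, and 0.2/0.075 = 2.667. With 29 df, power is **83.1% one-sided** and **73.2% two-sided**. The 83% is therefore a one-sided Balaam figure. Dropout: 32/0.8 = 40, as stated.

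**2. The paired t-test of 2.1.** If 15% is the SD of the paired difference, 80% power needs 6 pairs (one-sided) or 7 (two-sided). If that SD is 0.15 × √2 = 0.212, it needs 9 or 11. After 20% dropout this is between 6/0.8 = 7.5, so 8 children, and 11/0.8 = 13.75, so 14. This test does not lead to 40.

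**3. The independent t-test of 8.2 on raw period-end values.**

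- Both periods pooled, 32 v 32 records: SE = √(2 × 0.15²/((1 − rho) × 32)), 62 df. With equal sequences the positive covariance from A and D cancels the negative covariance from B and C.
- One period, 16 v 16: SE = √(2 × 0.15²/((1 − rho) × 16)), 30 df.
- Comparator: mixed model with treatment, period, carryover and random child, generalised least squares SE, 28 df.

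| rho | Pooled t-test: SE, power | One period: power | Mixed model: SE, power |
|---|---|---|---|
| 0.5 | 0.053, 96% | 73% | 0.049, 98% |
| 0.7 | 0.068, 82% | 52% | 0.056, 93% |
| 0.8 | 0.084, 65% | 37% | 0.061, 89% |
| 0.9 | 0.119, 38% | 21% | 0.067, 82% |

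The pooled t-test matches the Balaam SE of 0.075 at rho = 0.75: √(2 × 0.0225/(0.25 × 32)) = 0.075. It is less precise only above that value.

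**4. The independent t-test on within-period changes.** Footnote 3 of 3.3 gives each period its own start and end actigraphy, so this reading is available. The SD of a change is 0.212 whatever rho is. Pooled: SE = 0.212 × √(2/32) = 0.053, power 96%. One period: SE = 0.212 × √(2/16) = 0.075, power 73%.

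**5. Type I error and carryover.** With equal completers per sequence, the pooled raw t-test has nominal size (4.9–5.4% in 20,000 simulated trials) and no carryover bias. With unequal completers (A and D equal, B and C equal), the ratio of true to assumed variance is 1 + rho × (nA − nB)/(nA + nB). For a hypothetical 10/6/6/10 this is 1.125 at rho 0.5 and 1.175 at rho 0.7, giving sizes of 6.4% and 7.0%. For 6/10/10/6 the ratios are 0.875 and 0.825, giving 3.7% and 3.2%. Simulation agrees to within about half a percentage point. In the 10/6/6/10 case, 12.5% of any carryover difference enters the estimate.

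**The case against.** Several points on the other side have force.

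- Raw values or changes, pooled or separate periods, and model terms are details that an SAP may settle, and only the protocol was available. That stands, and the point does not rest on their absence. It rests on the protocol naming one test in 8.2 and sizing the trial on others. An SAP can agree with at most one of the three statements.
- Section 2.1 does not name melatonin or say what is paired, so it could mean a before-after comparison. That is a fair reading. It still would not produce 40 children, and it would not size the comparison in the primary objective.
- Under-powering is not shown. This is correct: pooled changes give 96%, changes in one period match the Balaam SE exactly, and pooled raw values are worse than the Balaam contrast only above rho = 0.75.
- The gap between 83% and 73% comes from sidedness, not from the t-test. This is also correct, and it should be resolved as part of the same alignment.
- The departures in type I error and the carryover bias need unequal dropout between sequences, which the protocol does not predict. They show sensitivity and are not an expected result.

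**Conclusion.** The point holds and should be fixed. Sections 2.1, 8.1 and 8.2 name three different tests. The only one in 8.2 that compares treatments is not the one for which 83% power is claimed, and it carries neither the own-control nor the carryover argument of 1.2.4.

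For 32 completers, a difference of 0.2 and a within-subject SD of 0.15, two-sided power under the wording of 8.2 runs from about 21% to 96%. It depends on which records enter and, for raw values, on a correlation between 0.5 and 0.9, which is assumed. A crossover mixed model with carryover has 82% to 98% over the same range, and a smaller SE than the pooled raw t-test at every correlation examined.

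What is established is a mismatch between test and power, and an open choice of analysis. Loss of power, inflated type I error and bias are conditional and are not established.

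**What to change.** In 8.2, replace the independent t-test for the primary comparison by one analysis that uses both periods of each child. An example is a linear mixed model on period-end TST (mean of the seven nights) with treatment, period, carryover, baseline TST and a random child effect, reporting tPCS minus melatonin with a 95% confidence interval. The carryover term is needed if the claim in 1.2.4 of no bias under unequal carryover is kept. The mixed-model figures above include carryover but not baseline.

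State whether period-end values or changes are analysed. Rewrite 2.1 and 8.1 to refer to this analysis with one stated sidedness, and restate the power, with the assumed within-child correlation where the method depends on it. Word 3.1 so that it matches the four sequences in section 3. Label the Wilcoxon and repeated-measures ANOVA results as descriptive.

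The cost is wording in these sections and one recalculated power figure. No new data, visits or patients are needed for the change of test.

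### The only between-treatment test in Section 8.2, an independent t-test, takes no week-0 covariate and ignores period and repeated measurement of each child; a mixed model would use data already collected

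*Protocol*

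**What the plan says.** The primary objective (Protocol 1.4) is to "assess the effectiveness of tPCS in improving total sleep time by 20% in children with neurodevelopmental disorder, compared with using Melatonin". Section 1.2.4 describes the design: "The unique Two-Period, Four-Sequence (Balaam's) design is used in this crossover trial in which each subject serves as his or her own control". Section 8.1 bases the sample size on a within-subject standard deviation in that design.

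Baseline data are complete by design. Section 3 states: "At baseline (week 0), all patients will do a one-week sleep actigraphy and complete SDSC questionnaire". The actigraphy footnote to the visit schedule in Section 3.3 places recordings "at start of the sequence period (Week 0 and Week 6) and at the end of the sequence period (Week 4 and Week 10"), so each child has a recording before and at the end of each period.

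Section 8.2 then names the tests. Between treatments: "Independent t-tests will be conducted to compare differences in outcomes between the two treatment groups". The others work within children or within groups: "Wilcoxon signed-rank test will be used to compare continuous variables at start and end of treatment", and "One-way Repeated Measure ANOVA will be conducted to assess changes in outcomes and patient scores within the group across the timepoints". Further non-parametric tests are also within groups. The section names no covariate, period term or child effect, and does not say whether the t-test is applied to end-of-period values or to changes.

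**The concern.** An independent t-test has no place for a covariate. The week-0 recording enters the tPCS-versus-Melatonin comparison only if the outcome is a change score, and then with a fixed coefficient of one, which adds the noise of the baseline week. The tests that do use the start-of-period values do not compare treatments. The t-test also treats each child's two outcomes as if they came from different children, although the design was chosen so that children act as their own controls.

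The children are aged 4 to 16 with mixed diagnoses (Section 2.3), so large differences between them in total sleep time can be expected. A model can take out part of that spread. With 10 children per sequence, a chance imbalance at week 0 would pass directly into the estimate if end values are compared. The other actigraphy measures and the SDSC share the schedule and the test.

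**Working it through.** **Inputs.** From Section 8.1: difference 0.2; within-subject SD 0.15 (variance 0.0225); 32 evaluable children, so 8 in each of four sequences. Assumed: one correlation, rho, between any two total-sleep-time measurements on a child, from 0.3 to 0.7. The protocol gives none, and a within-subject SD alone does not determine it. Total variance is then 0.0225/(1 − rho). Power is by noncentral t at two-sided 5% unless stated.

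**The plan's own figure.** Section 8.1 says "a sample size of 32 achieves 83% power at a 5% significance level". With fixed child effects, period and carry-over in Balaam's design, SE = 0.15 × √(2/8) = 0.075 on 29 df. Power is 83.1% at one-sided 5% and 73.2% at two-sided 5%, so the figure reproduces one-sided only (sidedness is a separate matter). Also 32/(1 − 0.2) = 40. This is a purely within-child calculation. A single week-0 value is constant within a child and cancels from it, so the gains below cannot be set against this 83%.

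**Single-period comparison, 16 v 16.** As multiples of the total variance: end values 1, change scores 2(1 − rho), baseline-adjusted 1 − rho². Adjustment removes rho² against end values and (1 − rho)/2 against change scores.

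| rho | Removed v end values | Removed v change | Power, end values | Power, change | Power, adjusted |
|---|---|---|---|---|---|
| 0.3 | 9% | 35% | 86.3% | 73.3% | 89.2% |
| 0.5 | 25% | 25% | 73.3% | 73.3% | 84.5% |
| 0.7 | 49% | 15% | 51.6% | 73.3% | 79.8% |

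At rho 0.5 the total SD is 0.15/√0.5 = 0.212. Both t-tests have SE 0.212 × √(2/16) = 0.075; adjustment gives 0.075 × √0.75 = 0.065.

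**Both periods in a pooled t-test, 32 v 32 observations.** End values at rho 0.5: SE = 0.212 × √(2/32) = 0.053, power 96% (99% at rho 0.3, 82% at rho 0.7). Change from each period's own baseline: SE = 0.15 × √2 × √(2/32) = 0.053, power 96% at every rho.

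**Both periods, random child effect.** Groups A and D never switch treatment, so they inform the treatment contrast between children, where the covariate helps. Write the variance of a child's mean as k × 0.0225. Then k = rho/(1 − rho) + 0.5 without the covariate. With it the residual child variance is rho × 0.0225, so k = rho + 0.5. With 8 children per sequence and period in the model, the precision of the treatment effect multiplied by 0.0225 is:

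- without carry-over: 8 + 4/k
- with carry-over: 8 + 4/k − (4 − 2/k)²/(4 + 2/k)

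| rho | k, without → with covariate | No carry-over term | Variance cut | Carry-over term | Variance cut |
|---|---|---|---|---|---|
| 0.3 | 0.929 → 0.8 | 12.31 → 13.00 | 5% | 11.75 → 12.65 | 7% |
| 0.5 | 1.5 → 1.0 | 10.67 → 12.00 | 11% | 9.33 → 11.33 | 18% |
| 0.7 | 2.833 → 1.2 | 9.41 → 11.33 | 17% | 7.11 → 10.37 | 31% |

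At rho 0.5 without carry-over, SE goes from 0.15/√10.67 = 0.0459 to 0.15/√12 = 0.0433, and power from 98.8% to 99.4%. With carry-over, SE goes from 0.15/√9.33 = 0.0491 to 0.15/√11.33 = 0.0446, and power from 97.6% to 99.1%. At rho 0.7 with carry-over, SE goes from 0.15/√7.11 = 0.0563 to 0.15/√10.37 = 0.0466, and power from about 93% to 99%.

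Set against the pooled t-test at rho 0.5, SE falls from 0.0530 to 0.0459 once period and child are modelled, and to 0.0433 with the covariate. The larger step comes from respecting the crossover.

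**The case against.** The strongest reply has four parts.

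*The figures depend on an unstated correlation.* This stands. A reader might infer that about a quarter of the variance is left in the primary comparison. That holds only at rho 0.5 in a single-period comparison, and the protocol neither gives nor implies that value.

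*A period-1 analysis is not what the protocol describes.* This stands too. The rise in power from 73% to 84% is tempting to quote, but it needs 16 v 16 children in period 1 alone and rho 0.5. Outcomes are scheduled in both periods and Section 8.1 powers on both. With both periods pooled, even the t-test has 96% power at rho 0.5. If 0.15 is read as the total SD, the 16 v 16 t-test already has about 95% power, and adjustment at rho 0.5 adds about 3 points.

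*The t-test may be on change scores.* It may. The wording of 8.2 allows it, and an objective framed as improvement points that way. The comparison cannot therefore be called wholly unadjusted, and the imbalance concern is confined to end values. Change scores remain less efficient than adjustment at every rho below 1.

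*Covariates are a matter of preference, are often left to an analysis plan, and cancel in a crossover.* This does not carry. The protocol has itself fixed a test that cannot take a covariate. Cancellation holds for fixed child effects. With a random child effect the gain survives, because half the children never change treatment.

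**Conclusion.** The point holds as a free improvement. Section 8.2 fixes a between-treatment test that takes no baseline covariate and disregards period and repeated measurement, although the week-0 recording exists for every child and the protocol justifies and sizes the trial on a within-subject crossover.

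For rho 0.3 to 0.7 under equal correlations, the covariate is worth 5% to 17% of the variance in a two-period mixed model without carry-over and 7% to 31% with it. In a single-period comparison it is worth 9% to 49% against end values, or 35% to 15% against change scores. Under the 8.1 inputs the benefit is chiefly a narrower interval and protection against chance imbalance. Power in the mixed model at rho 0.5 is already about 98% to 99%.

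The documents do not support the inference that the missing covariate leaves the trial underpowered, or that it biases the comparison: under randomisation the t-test is not biased for want of a covariate. That 8.2 lacks the covariate and the crossover terms is certain; the size of the gain is only as good as the assumed rho.

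**What to change.** In Section 8.2, replace the independent t-test on total sleep time by a linear mixed model with treatment, period, a random child effect and week-0 mean total sleep time as covariate. State whether a carry-over term is included, since Section 1.2.4 appeals to unequal carry-over in choosing the design. Use week 0 and not week 6 as the covariate, because week 6 follows randomised treatment. Analyse the other actigraphy measures and the SDSC in the same way, each with its own week-0 value. The Wilcoxon and repeated-measures analyses can stay as within-group descriptions.

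The cost is a wording change and one degree of freedom for the covariate. No visit, measurement or child is added.
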